**For Protocol Office use only:**

Protocol title: The Effects of Hyperbaric Oxygen on  
Rheumatoid Arthritis: a Pilot Study.  
FDG20160004H wAMD13

investigator name redacted 28 Jan 20

DGMC Human Research Protocol Template

exclusively to the study. Access will be granted only to study personnel.

To be in compliance with Government regulations study personnel will utilize 128 bit AES encryption. AES is widely used across the government healthcare sector to secure data-at-rest, data-in-motion and data-in-transit. All data transfers will be made via (password protected CD, encrypted Electronic Mail, Secured FTP server, other). All data files will utilize the Advanced Encryption Standard approved cryptographic algorithm used to protect electronic data.

**Hard Copy Records:** A copy of the IRB approved informed consent signed and dated by the volunteer and designee will be provided to the study volunteer. The original signed and dated IRB approved informed consent form will be placed with other study records, in a locked cabinet and secured area within the IRB Protocol Office at the Clinical Investigation Facility. A copy of the signed ICD will be in the coordinator offices located in the Internal Medicine Clinic. These records will be accessible only to study personnel, the IRB, and employees of authorized Federal departments and regulatory agencies. Duplicates will be provided to the volunteer upon written request.

All subjects will be treated in compliance with DODI3216.02\_AFI 40-402 and applicable FDA and DHHS guidelines.

All biologic specimens will be maintained at David Grant Medical Center and will be handled and disposed of in accordance with federal regulations.

**6.8. Data Collection/Analysis:**

**This is a pilot study with 10 participants with complete data sets**

Demographic information will be collected including sex, age and ethnic background in accordance with HIPPA compliance.

Data collected during this study will be analyzed at various points in time to include physician exams, labs (CRP, ESR, Basic Metabolic Panel, analysis of Microparticles, neutrophil and platelet activation, radiologic studies, joint inspection.

Changes in joint pain will be determined by self-reporting and results of the standard outcome measures questionnaires (the RAPID 3, PSQ-3 and Visual Analog Scale for pain).

A separate sleep survey will be administered.

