#### **6.4. Research Design and Methods:**

HBO2 can be administered either in the multiplace chamber, or the monoplace chamber. The multiplace chamber is compressed with air, and the patients breathe oxygen through hoods or masks. The monoplace chamber is pressurized with oxygen, so that the patient breathes the ambient oxygen. Only the delivery system is different. There is no difference in the oxygen delivered, or in attendant risks.

This is a pilot study.

1. Patient eligibility will be determined by the Rheumatologists, specialists in diagnosing rheumatoid arthritis. Recruitment will take place from their pool of patients. Additionally, patients that have been seen in the military treatment facility (MTF) within the past year with a diagnosis of rheumatoid arthritis will be contacted, after obtaining IRB-approval with a HIPAA waiver. Patients will be recruited if they: diagnosed with rheumatoid arthritis meeting ACR/EULAR 2010 classification criteria and any one of the following:
  - a. Patient does not want to be on rheumatologic medications.
  - b. Patient has contraindications to standard rheumatologic medications.
  - c. Patient has failed treatment or an incomplete response with standard rheumatologic medications.
2. The initial screening visit after the rheumatologist has discussed the trial will be the consenting and review of the inclusion/exclusion criteria. After the consent is signed the Hyperbaric physician will do a physical examination, review of inclusion and exclusion criteria and medication review to determine if it is safe for the subject to receive HBO2. An HCG by point of care testing (POCT) will be completed by the coordinator in women capable of pregnancy. After this exam is done the subject will be scheduled for a trial hyperbaric session.
3. The visit window timeline for screening, Baseline, and first HBO2 treatment to occur all within one month (four weeks) before start of HBO Hyperbaric Therapy Session.
4. **Baseline** The Baseline date is dive #1 date. This visit includes:
  - A visit with the rheumatologist to do routine assessments to establish baseline measurement using the the Disease Activity Scale (DAS28)
  - Labs (CRP and ESR, Basic Metabolic Panel (BMP) and Microparticles) will be done. A MRI with and without contrast and ultrasound will be done on both hands

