**Number of Subjects:**

- Total Number of Subjects: 20
- Number of Subjects Planned for DGMC: 20

A total of up to 20 subjects will be recruited. We will continue to recruit and treat until 10 complete data sets have been obtained. In the event that ten total data sets are obtained and additional subjects are in the process of the intervention, at the PI's discretion, those additional subjects will receive full treatment.

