**8. Investigation Schedule**

	Y1 Q1	Y1 Q2	Y1 Q3	Y1 Q4	Y2 Q1	Y2 Q2	Y2 Q3	Y2 Q4
Recruitment	X	X						
Enrollment	X	X	X					
Baseline Data		X	X	X				
Treatment			X	X	X	X		
Data Collection			X	X	X	X		
Statistical Analysis					X	X	X	
Publications/Reports						X	X	X

**9. Use of Investigational Drug(s)**       No       Yes

**10. Use of Investigational Device(s)**       No       Yes

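### Section 8 schedules analysis and reports before outcome collection ends, with no data cut-off, and its rows do not fit the visit plan or the recruitment rule

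*Combined protocol and SAP*

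**What the plan says.** Section 8 is a chart of eight quarters. The row "Statistical Analysis X X X" covers Y2 Q1 to Q3, and "Publications/Reports X X X" covers Y2 Q2 to Q4. The row "Treatment X X X X" covers Y1 Q3 to Y2 Q2, and Data Collection has the same four quarters. Recruitment is marked in Y1 Q1 and Q2, Enrollment in Y1 Q1 to Q3, and Baseline Data in Y1 Q2 to Q4.

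Section 6.8 states that "Data collected during this study will be analyzed at various points in time" and then lists examinations, laboratory tests and imaging. It names no test, cut-off, data lock or interim look, and does not say who may see results.

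Section 6.4 fixes the visit times. Item 4 says "The Baseline date is dive #1 date". Item 6 requires 30 sessions within 10 weeks. Item 9 places the month-6 visit six months after baseline, with a window of two weeks either side.

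Section 6.6 (Number of Subjects) allows up to 20 subjects and says "We will continue to recruit and treat until 10 complete data sets have been obtained".

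**The concern.** The chart has analysis, and then reporting, under way while subjects are still being treated and scored. Only one treated group is described, with no sham arm and no blinding. The rheumatologist scores DAS28, study team members administer the questionnaires, and section 6.7 has the team follow endpoints in real time. Pooled results seen midway could affect how later visits are scored. They could also affect which analyses are chosen, since none is specified. Section 4 wants an effect size from this pilot to plan a larger study, so a figure taken from early subjects could misinform that study.

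The second problem is that the rows cannot all be true together under the visit plan. The chart therefore does not show when the last month-6 visit happens, or whether Data Collection is still open to receive it.

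**Working it through.** **Conventions.** Quarter = 91.25 days; six months = 182.6 days. Y2 Q1 starts at day 365 (month 12), Y2 Q2 at day 456.25 (month 15), and Y2 Q2 ends at day 547.5 (month 18). The shortest course, 30 sessions on consecutive weekdays, runs from the first Monday to the sixth Friday: 5 × 7 + 4 = 39 days. The longest is 70 days.

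**1. The chart's own end date.** Last baseline at month 12, plus 6 months = month 18, the end of the Data Collection row. The chart's figure is reproduced, with zero slack.

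**2. Overlap.** Analysis starts at month 12 and collection ends at month 18: 6 months. Reports start at month 15: 3 months.

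**3. If the Baseline Data row is right.**
- Last session: 365 + 70 = day 435 at the latest, which is in Y2 Q1. The Treatment mark in Y2 Q2 then has nobody in it.
- Last nominal month-6 visit: 365 + 182.6 = day 547.6, against closure at day 547.5.
- End of its window: 547.6 + 14 = day 561.6. That is 2 weeks past Data Collection but before Statistical Analysis ends (day 638.75).

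**4. If treatment does run into Y2 Q2.** Days late = last session − course length + 182.6 − 547.5.
- Last session on the first day of Y2 Q2, 70-day course: 456.25 − 70 + 182.6 − 547.5 = 21.35 days, or 3.1 weeks. A visit 14 days early is still 7.35 days late.
- Same last session, 39-day course: 52.35 days, or 7.5 weeks.
- Last session on the last day of Y2 Q2, 70-day course: 547.5 − 70 + 182.6 − 547.5 = 112.6 days, or 16.1 weeks.
- Same last session, 39-day course: 143.6 days, or 20.5 weeks.

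The range is about 3 to 20 weeks, depending on where in the quarter treatment ends.

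**5. If the Enrollment row is right.** 273.75 + 28 (screening to first session) + 182.6 + 14 = day 498.35. The whole window closes 7 weeks before Data Collection does.

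**6. The recruitment rule.** Baseline data start at month 3, so the earliest complete data set is at 3 + 6 − 0.46 (two weeks early) = month 8.5. If first sessions start with the Treatment row, at month 6, it is month 11.5. Recruitment ends at month 6, before any complete set can exist. For ten sets to exist when Enrollment ends at month 9, all ten subjects would need baseline by month 9 − 6 + 0.46 = 3.46, that is, in the first two weeks of the Baseline Data row.

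**7. Share with nominal month-6 data, assuming even accrual (my assumption).**
- Baselines over months 3 to 12: (6 − 3)/9 = 33% when analysis starts and (9 − 3)/9 = 67% when reports start.
- Baselines over months 3 to 9.92 (Enrollment row plus four weeks): 3/6.92 = 43% and 6/6.92 = 87%.
- First sessions from month 6 (Treatment row): essentially none when analysis starts.

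**The case against.** The strongest reply is that this is a coarse planning chart. A mark shows activity at some point in a quarter, the nominal last visit fits on the Baseline Data row, and the Enrollment row fits with seven weeks to spare. Items 3 and 5 of section 6.4 can also be read as letting baseline assessments precede the first session by up to four weeks. Then 365 + 28 + 70 = day 463, just inside Y2 Q2. If month 6 were counted from that assessment, the visit would still fall at day 547.6. All of this stands. It means that the lower end of the 3-to-20-week range depends on item 4's definition of baseline.

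Three stronger readings are tempting, and the documents do not support them.

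- *The schedule leaves no time for the last month-6 visits.* That follows only if treatment runs into Y2 Q2. On the Baseline Data row only the late window spills over, and it is still inside the analysis period.
- *Interim results will steer the study.* No such use is planned. Section 6.4 stops treatment at 30 sessions whatever the response, section 6.7 ties closure to safety events, and recruitment depends on completeness. Enrollment is scheduled to close three months before analysis starts. The principal investigator's discretion in section 6.6 concerns subjects already in treatment and is not linked to results. The clinicians also see each subject's response anyway, so the extra bias from a pooled look cannot be sized.
- *Repeated looks inflate the false-positive rate by a known amount.* No test, significance level or number of looks is stated, so no rate can be computed.

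Nor does a report begun in Y2 Q2 have to rest on early subjects only, because its row runs to Y2 Q4. What the reply does not remove is the overlap, the missing cut-off and the conflict between rows.

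**Conclusion.** The point holds as a planning defect that should be corrected. Analysis is scheduled six months, and reporting three months, before outcome collection ends, with no stated cut-off or lock. These figures come straight from the section 8 chart and do not depend on how section 6.8 is read.

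The rows conflict with the visit plan. With baseline at the first session, either the Treatment row runs too long, or the last month-6 visits fall about 3 to 20 weeks after Data Collection closes. The Recruitment and Enrollment rows also cannot realistically accommodate recruiting until ten data sets are complete. Following that rule would push accrual and month-6 visits later.

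The effect on results is a possibility: coloured scoring at later unblinded visits, or analyses chosen after seeing early data. Its size cannot be estimated from the documents. The shares of 0 to 43% of subjects with month-6 data when analysis starts are illustrative and rest on even accrual.

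**What to change.** In section 6.8, state that there will be one efficacy analysis, after the last month-6 visit and data lock, and that before then only accrual, data completeness and adverse events will be tabulated. Safety review continues as section 6.7 describes.

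In section 8, reconcile the Recruitment, Enrollment, Baseline Data and Treatment rows with each other, with the definition of baseline in section 6.4, and with the ten-data-set rule in section 6.6. Extend Data Collection past the last month-6 window: into Y2 Q3 if the Baseline Data row stands, or into Y2 Q4 if treatment runs to the end of Y2 Q2. Start the efficacy analysis after that, and reports after the analysis.

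The cost is one sentence and a corrected chart. First results come one to two quarters later. If treatment does run to the end of Y2 Q2, the last window can close as late as 547.5 + 143.6 + 14 = about day 705. That is 25 days before the eight quarters end, so the chart itself may need to be lengthened.

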**Source of Research Material per Participant:**

Source of Research Material per Participant	Standard Care	Research Driven
Blood Sample – ESR	0	5
Blood Sample CRP	0	5
Metabolic Panel	0	3
Microparticles	0	5
Ultrasound/ MRI	0	3
Questionnaires	0	9

Lab sample for analysis of Microparticles, neutrophil and platelet activation will be sent to:  
 name/contact information redacted 28 Jan 2020

**7. Conflict of Interest**

NONE.

**8. Investigation Schedule**

	Y1 Q1	Y1 Q2	Y1 Q3	Y1 Q4	Y2 Q1	Y2 Q2	Y2 Q3	Y2 Q4
Recruitment	X	X						
Enrollment	X	X	X					
Baseline Data		X	X	X				
Treatment			X	X	X	X		
Data Collection			X	X	X	X		
Statistical Analysis					X	X	X	
Publications/Reports						X	X	X

**9. Use of Investigational Drug(s)**       No       Yes

**10. Use of Investigational Device(s)**       No       Yes

**11. Support Required**

**Pharmacy Support:** Non applicable, no medications will be given.  
 Contact the pharmacy early in protocol development phase of your study if drugs are involved.

Drug or Placebo	Investigational?	Which pharmacy will prepare?	Support letter attached?
N/A	N/A	N/A	No

**Lab Support:**

Request CLIA certificates from all laboratories for your files.

Test Name	Standard Care?	Which lab will perform each test?	Support letter attached?
CRP	No	DGMC	Yes
ESR	No	DGMC	Yes
Metabolic Panel	No	DGMC	Yes
Microparticles	No	University of Maryland	N/A

**For Protocol Office use only:**

Protocol title: The Effects of Hyperbaric Oxygen on  
Rheumatoid Arthritis: a Pilot Study.  
FDG20160004H wAMD13

investigator name redacted 28 Jan 20

DGMC Human Research Protocol Template

**Radiology Support Required:**

**If radioisotopes or radiation-producing equipment will be used, describe here.**

Procedure	Standard Care?*	Which facility will perform proc.?	Support letter attached?
Ultrasound	No	DGMC	Yes
MRI	No	DGMC	Yes

\* Any Radiation exposure that is not standard care requires Radiation Safety Committee review.

**Nursing Support:** N/A

**CIF Support:** Consultation, biostatistics, research coordination and administrative support.

**Other Support:** Hyperbaric Clinic participation for the administration of 30 HBO2 sessions with accompanying monitoring.

**12. Budget, Equipment, and Supplies**

Requesting Funds:  Yes  No

R&D  O&M  HMJ  OTHER (explain source):

Study Year	Item Description	Unit of Issue (UOI)	Cost/UOI	Quantity	Total Cost
2016	N/A				
2017	Labs for Microparticles		55	50	2750.00
2017	Fed Ex		28.90	50	1445.00
2018	Labs for Microparticles		55	30	1650.00
2018	Fed Ex		28.90	30	867.00

I understand that the funding is the responsibility of the PI, which includes; management, tracking, recording and must be reported to the IRB annually with your continuation report

**For Protocol Office use only:**

Protocol title: The Effects of Hyperbaric Oxygen on  
Rheumatoid Arthritis: a Pilot Study.  
FDG20160004H wAMD13

investigator name redacted 28 Jan 20

DGMC Human Research Protocol Template

9. Recruitment flyers
10. Surveys (DAS28, PSQ-3, VAS scale for pain using a grid & numbers)
11. MRI Screening form
12. RAPID 3
13. HIPAA Waiver
14. Patient Letter

